### **Medical Record Review**

The medical record of all clinical patients will be reviewed by the investigators after the completion of their flap procedure to identify intra- and post-operative findings that may be correlated to pre-operative imaging data. Patient (age, obesity, radiation, chemotherapy, smoking, and other medical comorbidities) and surgical factors (flap type, laterality, and surgical time) that are known to affect free flap procedure outcomes will be collected.

### **Data Analysis**

Standard postprocessing techniques including but not limited to noise filtering, co-registration to anatomical images, and 3D rendering will be applied to the optimal MRA images before the data are presented to the investigators for further analysis. The clinical CTA data will only be postprocessed with a 3D rendering algorithm because they already contain basic anatomical information.

De-identified optimal MRA and CTA data will be presented, in a randomized order, to the investigators for their independent assessment.

The radiologists will assess the imaging data on the following aspects:

- Imaging artifacts;
- Noise Level;

- Any other findings that may affect clinical interpretation of the images.

The plastic surgeons will assess the imaging data on the following aspects:

- The overall image quality;
- Anatomy accuracy;
- Vascular network continuity;
- Perforator branching pattern;
- Clinical applicability;
- Any other findings that may affect the planning, or the execution, or the follow up strategy of the flap procedure.

The plastic surgeons will also identify target perforators that are suitable to build a flap upon. An investigator will make the following quantitative measurements on each target perforator using a commercial workstation or custom-built software:

- Signal-to-noise ratio (SNR);
- Contrast-to-noise ratio (CNR) to muscle and fat;
- Perforator size;
- Length of the Perforator Intramuscular Course;
- Any other quantitative metrics that may support clinical decision-making.

#### Statistical Analysis

Statistical comparison between the optimal MRA and CTA data sets will be performed with appropriate testing methods and multi-comparison correction using standard statistical software packages.

Summary statistics will also be calculated for the quantitative measurements obtained from the MRA data set. These summary statistics will serve as the pilot data for sample size calculation in future clinical trials.

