## OBJECTIVE

The perforator flap is a new improvement in reconstructive microsurgery that is increasingly gaining popularity in many different reconstructive applications to breast, torso, and extremities [Saint-Cyr 2009; Geddes 2003]. Because there is considerable inter-patient variation in the number, size, and position of perforator vessels, success of perforator flap surgery relies on state-of-the-art preoperative planning based on detailed understanding of the three-dimensional (3D) structure of the associated vasculature. Currently, computed tomography angiography (CTA) is the method-of-choice for preoperative vascular imaging in breast reconstruction surgeries. While CTA is capable of generating excellent anatomical details of perforator vessels, patients are also exposed to additional risks associated with the use of ionizing radiation and iodinated contrast agents. Magnetic resonance angiography (MRA) using intrinsic contrast mechanisms (without the use of any external contrast medium), such as velocity-encoded phase contrast, can generate accurate, high-resolution 3D vasculature maps without the risks associated with CTA. Therefore, non-contrast MRA is a more desirable alternative to CTA in preoperative planning of flap surgeries.

The overall objective of this pilot study is to develop and optimize preoperative MRA imaging protocols for various perforators commonly used in flap surgery with phantom and healthy volunteers, and to obtain clinical validation of the optimized protocols with a group of patients receiving flap surgery at the OSU Wexner Medical Center. Data obtained in this study may also serve as the basis for statistical planning of future clinical trials.

Based on our previous experience with other magnetic resonance imaging (MRI) techniques, we hypothesize that optimal MRA images can only be obtained with a carefully selected combination of imaging hardware, acquisition, and postprocessing factors. The main objective of this pilot study is to

determine this optimal combination through the comparison of image quality between different combinations.

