The secondary objective of this pilot study is to evaluate, both qualitatively and quantitatively (for details see below), the quality of the optimized MRA images and compare them with clinical CTA images. Our hypothesis is that the quality of the optimized MRA images is at least comparable to that of the CTA images. The quantitative measurements obtained from this pilot population will also serve as the preliminary data for future studies and be used in statistical calculations that determine their study population.

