### **Clinical CTA Data Extraction**

For patient subjects who had at least one pre-operative CTA performed at OSUMC within the past 48 months, or will have at least one pre-operative CTA performed at OSUMC prior to a scheduled flap procedure, an investigator will review their CTA cases available on OSUMC PACS and select the most recent one for further comparison and evaluation.

For patient subjects who do not have any pre-operative CTA on OSUMC PACS and are not expected to get one within the next 24 months, a radiologist will review previously acquired CTA cases saved on OSUMC PACS that were obtained in the past 48 months, and select an age- and gender-matched case with clear depiction of the relevant perforator(s) for further comparison and evaluation.

Comparison with clinical CTA is not necessary for volunteer data acquired for protocol development and optimization purposes.

The selected CTA data set will be retrieved from the Ohio State University Wexner Medical Center Picture Archiving and Communication System (OSUWMC PACS) and downloaded to a research data server protected by secure password and firewall. The downloaded data will be immediately de-identified with validated software and verified by imaging Corelab staff.

On investigational images, any incidental findings will be shared with the participant and his/her primary care physician who was identified during the consent process. However, the investigational images are not diagnostic and do not replace usual care.

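### Does naming only MRA summaries as pilot data leave a later MRA-CTA trial without the figures needed to size it?

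*Protocol*

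**What the plan says.** The Statistical Analysis section of the protocol has two short paragraphs. The first plans a statistical comparison of the optimal MRA and CTA data sets, with suitable tests and a correction for multiple comparisons. The second adds: "Summary statistics will also be calculated for the quantitative measurements obtained from the MRA data set". It continues: "These summary statistics will serve as the pilot data for sample size calculation in future clinical trials".

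The Objective section describes the material for future planning twice, both times without naming a modality: "Data obtained in this study may also serve as the basis for statistical planning of future clinical trials" and "The quantitative measurements obtained from this pilot population will also serve as the preliminary data for future studies". Its secondary hypothesis is that optimized MRA is at least comparable to CTA in quality.

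Under Data Analysis, "De-identified optimal MRA and CTA data will be presented, in a randomized order, to the investigators for their independent assessment". The plastic surgeons pick target perforators, and "An investigator will make the following quantitative measurements on each target perforator using a commercial workstation or custom-built software". Under Clinical CTA Data Extraction, a patient with no CTA of their own, and none expected, is compared with another person's scan: the radiologist is to "select an age- and gender-matched case with clear depiction of the relevant perforator(s) for further comparison and evaluation".

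The protocol states no design, endpoint, margin, alpha or power for any future trial.

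**The concern.** Read alone, the second paragraph of the Statistical Analysis section ties future sample sizes to one modality. The hypothesis is comparative, and the protocol presents MRA as the alternative to CTA, so a natural next trial would compare the two, perhaps in the same patients. The size of such a trial depends on the SD of the within-patient difference. That needs the MRA SD, the CTA SD and their correlation, and MRA summaries supply only the first.

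Supplying planning figures is a stated purpose of the pilot. If the pilot reported MRA summaries and nothing else, the planner of a paired trial would have to guess the other two inputs, and the guess would drive the sample size.

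**Working it through.** **1. Is there a planned figure to reproduce?** No. The protocol gives no derivation for the 25 volunteers or the 50 patients, and no SD, correlation or margin. Everything numerical below is an assumption used for illustration.

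**2. Is the statistical premise right?** For a paired comparison, with k = CTA SD / MRA SD and r = within-patient correlation:

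- variance of the difference, in units of the MRA variance = 1 + k² − 2rk
- pairs = (1.960 + 0.842)² × (1 + k² − 2rk) / d²

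Assume d = 0.5 MRA SD (a difference to detect, or a margin with no true difference), 80% power and two-sided 5% (one-sided 2.5%). The multiplier is 7.849 / 0.25 = 31.40.

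| r | k = 1: factor | pairs | k = 1.5: factor | pairs |
|---|---|---|---|---|
| 0 | 2.00 | 63 | 3.25 | 103 |
| 0.3 | 1.40 | 44 | 2.35 | 74 |
| 0.5 | 1.00 | 32 | 1.75 | 55 |
| 0.7 | 0.60 | 19 | 1.15 | 37 |
| 0.9 | 0.20 | 7 | 0.55 | 18 |

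These are normal approximations; for k = 1 the noncentral t gives 65, 46, 34, 21 and 9. So the premise is right: a single MRA SD fits 7 to 103 pairs. This is a general property of paired designs. None of the inputs comes from the protocol.

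**3. Does the protocol confine the planning data to MRA summaries?** Set the statements side by side:

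- Statistical Analysis, first paragraph: MRA and CTA data sets are compared statistically. Comparing quantitative measurements would ordinarily produce estimates for both modalities and, where a patient has both scans, differences.
- Statistical Analysis, second paragraph: the word *also* places the MRA summaries on top of that comparison. The sentence does not say that only these summaries may be used.
- Objective: "The quantitative measurements obtained from this pilot population will also serve as the preliminary data for future studies". The pilot population is imaged by MRA and compared with CTA, so these words cover measurements from either.

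The statements can all be followed at once. The specific sentence is narrower than the general ones but does not contradict them.

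**4. What happens if the plan is followed as written?** The scans, readings, measurements and MRA-CTA tests are the same whether or not a table of CTA and paired-difference summaries is printed. The pilot's conclusions do not move. The protocol stores the coded MRA data and the selected CTA sets on research servers, so the SD of the difference could be obtained later for patients with their own CTA.

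**5. Would the extra figure be decisive?** The number of patients with their own CTA is not stated; it is at most the 50 evaluable patients. The 95% confidence limits of an SD, as multiples of the estimate, are √((n−1)/χ²) at the two tail points:

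- 50 patients: 0.84 to 1.25
- 25 patients: 0.78 to 1.39
- 10 patients: 0.69 to 1.83

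With few true pairs, the added SD would itself be a loose guide.

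**The case for a change.** The strongest case for the concern is that the protocol makes a choice here and does not merely stay silent. It names one data set, and "These summary statistics will serve as the pilot data for sample size calculation in future clinical trials" refers back to that data set alone. A comparison by unspecified tests does not promise an SD of the difference or a count of true pairs. Adding them would cost a few lines and no scans.

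Three features of the data would also need care in any paired summary. Some patients are matched to another person's CTA and give no within-patient difference. A patient may have several target perforators, and these may differ between modalities. MRA may be noise-filtered, whereas "The clinical CTA data will only be postprocessed with a 3D rendering algorithm because they already contain basic anatomical information", so SNR and CNR differences partly reflect processing.

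What stands is that the sentence names MRA only, that a paired trial would need more, and that extra tables would be cheap. That supports an optional addition, not a correction. The three features concern how the MRA-CTA comparison itself is carried out; they do not show that the sentence on summary statistics is wrong. Errors from treating several perforators per patient as independent are no evidence either, because the protocol nowhere proposes that analysis. The choice of descriptive tables, the rule for matching perforators and the handling of several values per patient belong to the statistical analysis plan, which may exist and is not shown.

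**Conclusion.** The concern does not hold. The Statistical Analysis section contains no wrong figure, no faulty rule and no conflict with the Objective section. It plans the MRA-CTA comparison, adds MRA summaries to it, and does not exclude other uses of the data.

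The effect on this pilot's own results is nil. Any loss to a later trial requires that the trial be paired, that its planner have only the MRA summaries, and that nobody return to the stored data. The protocol establishes none of these; MRA summaries could suffice for a single-arm MRA study. The range of 7 to 103 pairs rests wholly on assumed correlations, SD ratios, margin, power and alpha, and describes paired designs in general.

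This conclusion assumes that the comparison is reported with its usual estimates and that the link between a patient's MRA and own CTA is kept. Nothing in the protocol suggests otherwise.

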#### **Consent Procedures**

A printed copy of the Consent Form will be provided to the subjects for review at their initial visit to the MRI facility, or prior to this visit if requested by the volunteer. An investigator or study key personnel will review the Consent Form with each subject, and answer any question regarding the nature of the study, study procedures, risks and alternatives. Subjects will be informed that participation is voluntary and that they can withdraw from the study at any time. Subjects will then be asked to complete a written MRI Safety Screening Form under the guidance of an investigator or key personnel. The investigator/key personnel will collect signed Consent Form and MRI Safety Screen Form from the subjects, and determine whether the subject is eligible to participate in the study according to the inclusion/exclusion criteria specified above. A copy of the signed Consent Form will be provided to the subject for their records. The documents will be stored in a locked cabinet upon completion at the Wright Center of Innovation.

## **Compensation**

All patient subjects will be compensated with a \$40 gift card at the Wright Center of Innovation for each research MRI scan they participate. Those who come to the Wright Center but are not able to complete the research MRI scan (due to unforeseen medical reasons or equipment breakdown) will be still compensated. All patient subjects will be asked to sign a form as proof of receiving payment. By law, payments to subjects are considered taxable income.

Volunteer subjects will not be compensated for their participation.

## **Data Confidentiality**

Personally identifiable information in Consent Forms, HIPAA Forms, and MRI Safety Screening Forms will be kept in a locked cabinet in the research area in the Department of Radiology. Only authorized members of the research team will have access to these identifiable records.

The raw image data will be coded at the time of acquisition through the use of subject ID codes instead of subject names. The coded data will be saved on a password-protected data server behind a firewall. The data server is located in a locked server room with limited access to authorized personnel only. The research team may share coded data with collaborating investigators, MRI scanner and coil vendors, or the FDA.

## **Adverse Events**

No invasive procedure or extrinsic agent will be applied or delivered to the subjects participating in this study. All MRI sequences used in this study will be identical to those used in daily clinical standard of care practices. Therefore, the health risk to the participants will not be greater than that of patients receiving a standard care diagnostic MRI examination.

The United States Food and Drug Administration (FDA) classified MRI up to 8.0 Tesla as non-significant risk. Potential risks include:

- 1) Excessive heat deposition in tissue due to high specific absorption rate (SAR);
- 2) Undesired neural stimulation due to fast switching of magnetic field gradients;
- 3) Malfunction of functional implants whose operation can be interfered by the RF field or the magnetic field gradients;
- 4) Temporary or permanent hear losses due to loud acoustic noises.

In this study, these potential risks are minimized:

- 1) The Philips 3.0 Tesla MRI system has both hardware and software limits on the maximum SAR level to less than or equal to 4.0 W/kg. This is the FDA approved limit. Excessive heat deposition may happen on the surface or near the tip of metallic objects embedded in body. However, these subjects will be excluded from participating this study by the use of the MRI Safety Screening Form;

- 2) The Philips 3.0 Tesla MRI system operates within the FDA guidelines regarding time varying magnetic field gradients;
- 3) All MRI sequence to be used are included in the FDA released clinical system sequence packages;
- 4) According to our exclusion criteria, all subjects with any type of activatable implants will be excluded from participating this study;
- 5) Dual ear protections (i.e. ear plugs and headphones) will be provided to all subjects participating in this study. With these protections in place, the scanner noise level will be under the FDA limit for sound (140 dB peak or 99 dB average).

